Developing Text-based Support for Parents of Adolescents After an Emergency Department Visit

IRB Approval Date: January 2, 2024

NCT05058664

RESEARCH PROTOCOL

FULL STUDY TITLE: Developing text-based support for parents of suicidal adolescents after emergency department visits: A multi-component intervention pilot

SHORT STUDY TITLE: Developing text-based support for parents of adolescents after an emergency department visit

BACKGROUND

Suicide, the second leading cause of death among 13 to 17-year-olds in the United States,¹ is a major public health crisis. Emergency departments (EDs) increasingly serve as the first and only line of clinical contact for suicidal adolescents,²⁻⁴ many of whom experience post-discharge suicide attempts and related crises requiring return ED visits.⁵⁻⁷ Unfortunately, a considerable number of youth at risk for suicide seen in EDs do not link to outpatient treatment or, if they do, these services may be delayed or prematurely discontinued.⁸⁻¹¹ During this high-risk period, parents or other caregivers are often at the forefront of suicide prevention, yet they report feeling overwhelmed and unsure about how to best care for their child's post-discharge needs.¹²⁻¹⁴ Thus, intervening with suicidal youth and their families during or shortly after an ED visit offers a promising window of opportunity to prevent post-discharge crises.

Thus, to improve post-ED bridging care and reduce youth suicidal crises, we propose to develop and pilot an adaptive, text-based intervention targeting two interrelated domains: (1) supporting parents in promoting the safety and well-being of suicidal adolescents and (2) providing support directed at enhancing parents' own well-being.

Text messages offer an accessible continuity of care strategy after ED care, as they are nearly ubiquitous in the United States, ²² and have been used to support a range of behavioral and health outcomes. ²³⁻²⁷ Because suicidal adolescents are heterogeneous with respect to varying levels of suicide risk ^{33,34}—and parents may experience varying caregiving challenges and stress—a texting intervention should ideally be tailored to address parents' unique and changing needs. Aiming to maximize outcomes while minimizing burden, a Just-In-Time Adaptive Intervention (JITAI) is an intervention design that adapts the provision of mobile-based interventions to meet the dynamically changing needs of individuals in the "real" world. ^{35,36} This study will build the foundation for an effective JITAI for parents of suicidal youth by investigating the feasibility and acceptability of employing a microrandomized trial (MRT)—an experimental design used for optimizing JITAIs. ³⁸

STUDY PURPOSE

This study seeks to develop and pilot an adaptive, text-based intervention for parents of suicidal youth transitioning from ED care. The study will address an urgent need for efficacious continuity of care strategies for suicidal youth post ED care using a scalable approach. The study's aims are as follows:

Aim 1 (Non-Clinical Trial):

Finalize text-based intervention components in preparation for the pilot study. Drawing on theoretical and clinical considerations, as well as our preliminary parent focus group data, we will develop text messages focused on two domains: (1) messages encouraging parental provision of adolescent-focused (A-F) support (e.g., suicide prevention activities, communication, tips for supporting at-risk youth); and (2) messages providing parent-focused (P-F) support (e.g., affirmation, tips for parents' own well-being). Text messages will be iteratively refined based on input from experts and parents.

Aim 2:

2a: As part of Aim 2, Pilot the text-based intervention to demonstrate its feasibility and acceptability. Parents of suicidal adolescents seeking ED services will be randomized to one of three groups: a control group or one of two 6-week intervention groups receiving either the A-F or A-F plus P-F texting components. Beyond feasibility and acceptability, we will explore the effect of intervention groups on the proposed mechanism (parental self-efficacy) and distal outcomes (engagement in suicide prevention activities) assessed over 2-, 6-, and 12-weeks post ED visit. Follow-up youth outcomes (e.g., suicide attempt and ED visit) will also be explored.

2b: As part of Aim **2**, pilot an embedded MRT to inform the development of a JITAl for parents of suicidal youth. Because all elements of A-F are seen as essential, while P-F support may require adaptation, the A-F plus P-F arm will include an embedded MRT involving two daily randomizations to P-F message vs. no message conditions for the duration of the 6-week intervention. We will explore if, and when, the P-F message vs. no message condition influences within-person proximal outcomes (parental stress, mood) assessed daily for the 6 weeks.

Aim 1 is preparatory non-trial work to Aim 2 - the clinical trial.

METHODS

Participants and Study Enrollment Criteria: Participants will include adolescent-parent pairs recruited from Psychiatric Emergency Services (PES) at the University of Michigan. Research assistants will screen admission logs for participant eligibility based on adolescents' age (13-17) and presenting problem due to (1) last-week suicidal ideation and/or (2) recent (within a month) suicide attempt/behavior (actual, interrupted, aborted suicide attempt). Exclusion criteria will include (1) youth with severe cognitive impairment or altered mental status (e.g., psychosis, manic state), (2) youth with severe aggression/agitation, (3) no availability of a legal guardian, or (4) parents not owning a cell phone with text messaging capability. Eligible PES patients and their parents will be approached by research assistants for parent/guardian consent and adolescent assent during recruitment shifts.

Eligible participants who provide consent/assent will participate in Aim 1 or Aim 2. Separate consent/assent forms for Aim 1 and Aim 2 will be provided at enrollment. Methods specific to Aims 1 and 2 are described below.

Unless listed in the Primary Analysis under "Data Analysis for Aim 2" section, all outcomes and assessments are exploratory or ancillary.

Aim 1 (Non-Clinical Trial) Methods:

Initial Development of Text Messages: An initial "bank" of text messages for the A-F and P-F intervention components will be developed using an iterative process. This process will draw on (a) relevant theory, (b) best-practice recommendations, (c) content area knowledge, and (d) our research team's preliminary data drawn from previous focus groups conducted with parents of suicidal adolescents after ED discharge. The tone of the messages will incorporate Motivational Interviewing (MI) principles as an additional strategy to increase parents' self-efficacy and motivation to implement the suggested recommendations and tips for adolescent- and parent-directed support. Some messages will incorporate links to additional online resources or information.

Description of Components and Sample Messages:

Adolescent-focused support (A-F component): The A-F texting component will include content consistent with best-practice recommendations for parents to buffer youth against suicide risk. This will incorporate messages focusing on: (1) restricting access to lethal means; (2) recognizing and attending to suicide warning signs; (3) encouraging adolescent's use of coping strategies; (4) ways parents can support and assist the youth in using the safety plan; (5) monitoring and supervising the youth with sensitive queries about mood and suicidality; (6) responding in a sensitive manner to disclosures of distress and suicidality; (7) tips for communication; (8) providing emotional support and engaging in activities promoting connectedness; and (9) reminders about crisis resources.

Parent-focused support (P-F component): The P-F texting component will include content focused on providing parent-directed support (e.g., encouragement, affirmations), as well as tips for parents' self-care and own well-being.

Procedures for Obtaining Parent Feedback in Aim 1: Parents meeting inclusion/exclusion criteria, as described above, will be recruited during or shortly after their adolescent's ED visit. Parents will provide feedback during or following the ED visit using an online survey to maximize retention. We will compile parents' ratings of messages with regard to the extent to which each message was perceived positively (5-point scale ranging from "disliked a lot" to "liked a lot"). For each message, parents' specific feedback will also be solicited and used to modify or discard specific messages. Moreover, parents will be asked to provide their opinions regarding message content they would prefer to receive as well as the proposed structure of the text-based intervention (e.g., frequency and duration of text messages). Feedback will be obtained with a survey build using a Qualtrics survey system, and the survey will take approximately 20-30 minutes to complete. Participating parents will be compensated \$30, and their feedback will be used to finalize the bank of messages.

Aim 2 Methods:

Overview of Aim 2 Procedures:

After providing informed consent / assent, participants will be enrolled in the study. After completing a baseline survey, parent-adolescent pairs will be randomized to one of three groups: control (standard ED care), A-F texting component alone, or A-F in combination with P-F texting component. Parents randomized to either A-F or A-F plus P-F intervention groups will receive the text-based intervention over a course of six weeks following their adolescent's ED discharge. The P-F component includes an embedded MRT, which will allow us to examine the feasibility and acceptability of conducting an MRT, as well as explore if and under what conditions receiving the P-F message may be most beneficial. Participants who are randomized to receive the P-F texting component (as part of the A-F + P-F intervention arm) will be randomized twice each day (morning and evening) to either receive or not receive the P-F message at each randomization; at each randomization, the probability of either receiving or not receiving the P-F message will be 50%. As such, parents receiving the P-F component will receive between none and two P-F messages on any given day, on average receiving one P-F message on any given day. Over the course of the 6-week intervention, parents in the A-F condition will receive between 1-3 messages, based on randomization (on average, 2 messages each day).

Assessment Procedures for Aim 2:

Participating parents and adolescents will complete baseline assessment during the index ED visit. Parents and adolescents will be asked to complete baseline measures using Qualtrics on a study-provided tablet computer. Participants will also be provided the option of filling out the measures using a paper and pencil format if they prefer or if any technological difficulties are encountered that would

prevent the completion of the surveys on a tablet computer. Parents and adolescents will each receive \$10 for completing the baseline assessment. Follow-up assessments will be conducted approximately 2, 6, and 12 weeks after enrollment. Parents and adolescents will complete assessments at 2 and 6 weeks using online surveys (using Qualtrics software). Parents will be compensated \$20, and adolescents will be compensated \$15 for completing each of the two online surveys. The 12-week follow-up, which will be used to assess youth suicide attempts and return ED visits, will be conducted over the telephone by a trained research interviewer. Adolescents and parents will each receive \$30 for completing the 12-week assessment. Chart data will also be abstracted to obtain relevant clinical information (e.g. psychiatric diagnoses, reason for hospitalization, previous hospitalizations). Finally, parent satisfaction with intervention components will also be assessed.

Aim 2 assessments were not collected for assessing primary or exploratory outcomes unless noted within the Aim 2 data analysis section.

Baseline Assessments

Parents at Baseline:

- Demographics
- DERS-SF
- Parental Self-Efficacy Scale
- PSC-17
- Mental Health Service Utilization Scale
- Multidimensional Scale of Perceived Social Support
- PHQ-4
- PHQ-10
- CGSQ-SF7
- Family History Screen
- GF-FAD
- Social/Emotional Support
- PANAS
- Munich Chronotype Questionnaire
- Safety measures (home environment lethal means restriction)

Adolescents at Baseline:

- Demographics
- DERS-SF
- AUDIT-C
- C-SSRS
- NIDA-modified ASSIST
- NSSI
- PHQ-9
- GAD-7
- Brief Hopelessness Scale
- Self-Efficacy to Cope with Suicidal Thoughts and Urges Scale
- Self-Rated Expectations of Risk
- Parent-Family Connectedness Scale
- GF-FAD
- Parent-Family Connected Scale
- Pediatric Family Relationships

Follow-Up Assessments at 2, 6 and 12 weeks

Parents:

- Parents' engagement in suicide prevention activities
- Parental Self-Efficacy Scale (parental coping self-efficacy)
- Social/Emotional Support
- PHQ-4 (depression and anxiety symptoms)
- PHQ-10 (areas of functioning in daily life)
- CGSQ-SF7 (caregiver stress)
- PANAS (positive and negative affect)
- Mental Health Service Utilization Scale (only at 6 and 12 weeks)
- Intervention Feedback (only at 6 weeks)
- Multidimensional Scale of Perceived Social Support (only at 12 weeks)

_

Adolescents:

- Parents' engagement in suicide prevention activities
- PHQ-4 (depression and anxiety symptoms)
- PHQ-10 (areas of functioning in daily life)
- Brief Hopelessness Scale (hopelessness)
- Self-Efficacy to Cope with Suicidal Thoughts and Urges Scale (suicide coping self-efficacy)
- Self-Rated Expectations of Risk (perceived suicidal behavior risk)
- Parent-Family Connectedness Scale (perceived connectedness to parents/family)
- Pediatric Family Relationships (family support)
- Mental Health Service Utilization (only at 12 weeks)
- C-SSRS (only at 12 weeks)

Daily Surveys:

All parents will respond to brief daily surveys over the 6-week intervention. Two brief (1-2 min) online surveys will be sent to parents' phone each day (morning and afternoon/evening) via text message using a secure automated delivery system. Parents will be provided with approximately 2 hours to complete the daily survey. To increase adherence, parents will be provided with an incentive of \$2 for each daily survey. Items will be brief and drawn from known and validated scales.

Data Analysis for Aim 2:

Primary Analysis: We will obtain descriptive data related to intervention feasibility and acceptability as measured by: (1) percentage of eligible participants who agree to participate in the study, (2) percentage of participants who complete follow-up assessments, (3) of those randomized to the texting intervention, percentages of parents who remain active (i.e. do not request to stop receiving messages), and (4) parents' satisfaction with the intervention.

Exploratory Analyses: In exploratory analyses, we will explore the effect of intervention on the proposed mechanism of change (parental self-efficacy) assessed at 2-, 6-, and 12-weeks post enrollment, we will use multi-level analyses for continuous variables (linear mixed-effects models). We will also conduct exploratory analyses of the effect of intervention on the proposed distal outcome of parental engagement in supportive and suicide prevention activities, assessed at 2-, 6-, and 12-weeks post enrollment. Analyses will be conducted using an intent-to-treat approach. Finally, we will describe differences between intervention vs. control regarding youth suicidal behavior outcomes at the 12-week follow-up.

We will conduct exploratory analyses on the primary proximal outcome (parental stress) using a generalization of regression developed for analyzing MRT data, specifically developed to ensure unbiased estimated of effects of time-varying treatments (i.e. sending a P-F message vs. not) on a time-varying outcomes (i.e. parental stress). Finally, for the exploratory analyses on the secondary proximal outcome, i.e. parental positive and negative affect, we will also use the generalization of regression analyses to explore if, on average across participants, receiving the P-F message is associated with a decrease in parental negative affect and an increase in positive affect.

RISK MANAGEMENT

The use of trained research staff for completing assessments will ensure that any potential safety issues are identified and appropriately addressed in accordance with study protocol. The PI will closely supervise research staff. Ensuring that any potential safety issues are appropriately addressed will be enhanced by the availability of an on-call psychologist. To this end, the study will have a comprehensive Risk Management Protocol detailing guidelines for managing safety concerns, including responding to high suicide risk and appropriate documentation. In particular, adolescents' suicidal ideation and behavior will be assessed at the time of the 12-week assessment. Trained research interviewers conducting the assessments will complete an Action Plan, detailing criteria and steps for initiating consultation with an on-call psychologist and includes documenting whether or not a participant met the study's high-risk criteria. The on-call supervisor will be available by telephone during scheduled assessments in case an adolescent meets high suicide risk criteria (e.g., recent suicidal ideation with thoughts of method, suicidal intent and/or plan; and/or disclosure of suicidal behavior since index ED visit). An endorsement of responses items indicating a high level of risk will result in the research staff member initiating the Action, which specifies next steps (e.g., contact the adolescent's parent/guardian; contact the on-call psychologist; provide recommendations in consultation with the oncall psychologists; contact emergency services, if needed).

CONFIDENTIALITY

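### Does leaving return ED visits out of the Aim 2 analysis section call for a change to the plan?

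*Combined protocol and SAP*

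**What the plan says.** Under Study Purpose, Aim 2a states: "Follow-up youth outcomes (e.g., suicide attempt and ED visit) will also be explored". Assessment Procedures for Aim 2 gives the 12-week contact the same two events: "The 12-week follow-up, which will be used to assess youth suicide attempts and return ED visits". It is a telephone interview by a trained interviewer, completed by parents and adolescents.

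Under Data Analysis for Aim 2, the only commitment on youth outcomes is the last sentence of the first Exploratory Analyses paragraph: "we will describe differences between intervention vs. control regarding youth suicidal behavior outcomes at the 12-week follow-up".

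Two further sentences govern the status of outcomes. Just before the Aim 1 methods, the protocol says that, outside the Primary Analysis, "all outcomes and assessments are exploratory or ancillary". Assessment Procedures for Aim 2 adds: "Aim 2 assessments were not collected for assessing primary or exploratory outcomes unless noted within the Aim 2 data analysis section".

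In the lists under Follow-Up Assessments at 2, 6 and 12 weeks, no item is labelled as ED visits. The nearest is the service-utilization measure, given to parents at 6 and 12 weeks and to adolescents at 12 weeks.

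**The concern.** An outcome that the aims promise to explore is missing by name from the section that decides which outcomes count as exploratory. In most protocols that would be a plain omission. Here the second status sentence gives it a consequence, because an assessment not noted in the analysis section loses exploratory standing.

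Two details are also open. The text does not say whether any, psychiatric or suicide-related visits count, and it does not say which instrument in the 12-week interview records them.

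At stake is whether a reader could tell a planned report of ED visits from a selected one. If their status were settled after the groups had been compared, a favourable count could be reported and an unfavourable one left out. The Background makes the outcome visible by naming "post-discharge suicide attempts and related crises requiring return ED visits" among the events that motivate the study.

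**Working it through.** No arithmetic applies. The plan gives no figure on this point, and the documents contain no sample size, event rate or error rate to work from. The check sets the sections side by side.

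1. **Outcomes named under Data Analysis for Aim 2.** The primary items are four: agreement to participate, completion of follow-up, remaining active in the texting intervention, and parent satisfaction. The exploratory items are parental self-efficacy, parental engagement in supportive and preventive activities, youth suicidal behavior at 12 weeks, parental stress, and parental positive and negative affect. ED visits appear 0 times, and so does the service-utilization measure.

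2. **The literal chain.** ED visits are outside the Primary Analysis, so the first status sentence leaves two options, exploratory or ancillary. If they are not noted in the analysis section, the second status sentence removes exploratory. Ancillary remains, against Aim 2a's promise to explore them. Both sentences are needed for this result. The second does not use the word ancillary, and the first alone is compatible with Aim 2a.

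3. **Whether ED visits really are unnoted.** The analysis sentence refers to outcomes in the plural at the 12-week follow-up, and the assessment section says that this follow-up is for suicide attempts and return ED visits. Reading the sentence as shorthand for that pair is reasonable. The second status sentence also speaks of assessments, and the 12-week assessment is mentioned in the analysis section. Against this, the enrollment criteria use attempt/behavior for actual, interrupted or aborted attempts, and both Aim 2a and the assessment section list ED visits as a separate item. The text is therefore ambiguous and does not plainly contradict itself.

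4. **Whether the source is missing.** In part only. The source is the 12-week telephone follow-up with parent and adolescent. The instrument and the visit definition are not given. The service-utilization measure is planned 2 times for parents and 1 time for adolescents, 2 + 1 = 3 follow-up administrations, but the text does not say that it records ED visits.

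5. **What would change in the results.** Primary measures affected: 0 of 4. The plan says only that differences in youth outcomes will be described. It sets no test or threshold for them. The most that could vary is whether and how one descriptive count is shown, and which label it carries.

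**The case for a change.** The strongest case for acting is that the documents separate the two events. A youth can attempt suicide without an ED visit, or return to the ED in crisis without an attempt. Aim 2a introduces its pair as examples, but an example of what will be explored is still a commitment, and the assessment section repeats the pair without that qualifier. On the strict reading, reporting a group comparison departs from the status sentence, while omitting it departs from Aim 2a. One sentence would settle the matter.

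Much of this stands. The strict reading is available, the visit definition is open, and how differing parent and adolescent reports would be combined is not stated. These choices could move a count. Naming ED visits in the exploratory sentence would be tidy.

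It does not show that following the plan leads to a wrong result. Aim 2a and the stated purpose of the 12-week interview both point to reporting ED visits, and a competent analyst would do so with the definition used stated beside the count. A clarification could equally call the visits exploratory or ancillary. That either label would do shows that the gap is in how the plan is written down and does not touch the design or the analysis.

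**Conclusion.** No change is needed. The aims and the analysis section are not fully aligned on return ED visits, and a literal reading of the two status sentences leaves those visits ancillary. The effect is confined to the label and definition of one descriptive, exploratory youth outcome in a pilot whose primary analysis is feasibility and acceptability. No primary measure, estimate or conclusion depends on it, and no bias can be sized from the documents.

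This rests on two assumptions. The first is that the 12-week interview does record return ED visits, as its stated purpose implies; the interview items are not shown. The second is that the analysts treat Aim 2a as binding, report the visits by group whichever way they fall, and state the definition used. Both are ordinary practice, and nothing in the documents points against them.

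### Does counting parents as active when they have merely not asked to stop messages make primary measure (3) wrong?

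*Combined protocol and SAP*

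**What the plan says.** The Primary Analysis paragraph of Data Analysis for Aim 2 names four descriptive indicators of intervention feasibility and acceptability: uptake among eligible participants, the "percentage of participants who complete follow-up assessments", the "percentages of parents who remain active (i.e. do not request to stop receiving messages" among those randomized to texting, and parents' satisfaction. The third is the one in question. Its only criterion is the absence of a stop request, and no other part of the protocol adds reading, replying, link use or delivery.

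Satisfaction has a matching entry in the parents' follow-up list, "Intervention Feedback (only at 6 weeks" as that list words it. The items are not reproduced.

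Daily surveys are described under their own heading, apart from the 2-, 6- and 12-week assessments: "All parents will respond to brief daily surveys over the 6-week intervention". They go to the parent's "phone each day (morning and afternoon/evening) via text message using a secure automated delivery system". Payment is part of the design: "To increase adherence, parents will be provided with an incentive of" $2 per survey. Aim 2b relies on daily data, since it concerns "within-person proximal outcomes (parental stress, mood) assessed daily for the 6 weeks". The overview of Aim 2 procedures says of the embedded MRT, "which will allow us to examine the feasibility and acceptability of conducting an MRT".

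**The concern.** To most readers, *active* suggests that a parent is still using the intervention. Measure (3) cannot show that. A parent who mutes the messages in the first week and never asks to stop is counted in the same way as one who reads every message.

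The other three measures do not clearly make up the difference. Uptake is settled before any message is sent. Follow-up completion concerns three scheduled assessments. Satisfaction is collected once, from items that cannot be seen. Response to the daily surveys, the densest record of parents' behaviour during the six weeks, is in none of the four.

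At stake is how the pilot's feasibility would be read. A high figure for measure (3) could be cited as sustained engagement when deciding whether to build a larger trial. The study also sets out to examine whether an MRT can be run, and that depends on parents answering the daily surveys that supply its outcomes.

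**Working it through.** The protocol states no target, threshold, sample size or expected rate for measure (3), so there is no planned figure to reproduce. The check is of definitions, with simple arithmetic.

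**1. What measure (3) computes.** Let *s* be the share of parents randomized to texting who ask to stop. Measure (3) = 1 − *s*. Nothing else enters it.

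**2. How far it could differ from a stricter reading.** Let *q* be the share of the remaining parents who answer no daily survey. The share who have neither asked to stop nor fallen silent is (1 − *s*)(1 − *q*), so the gap is (1 − *s*) × *q*. Both *s* and *q* are assumptions; the protocol gives neither. With *s* = 5%:

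| Assumed *q* | Measure (3) | (1 − *s*)(1 − *q*) | Gap (points) |
|---|---|---|---|
| 0% | 95% | 0.95 × 1.00 = 95.0% | 0 |
| 10% | 95% | 0.95 × 0.90 = 85.5% | 9.5 |
| 30% | 95% | 0.95 × 0.70 = 66.5% | 28.5 |
| 50% | 95% | 0.95 × 0.50 = 47.5% | 47.5 |

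Over *s* from 0 to 10% and *q* from 0 to 50%, the gap runs from 0 to 50 points. This shows only that the two quantities differ. It does not show that measure (3) misstates message use, because survey silence is not the same as ignoring messages.

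**3. Whether survey response could stand in for message use.** Scheduled surveys per parent: 6 weeks × 7 days × 2 per day = 84, or 14 per week. Maximum payment: 84 × $2 = $168. Three features of the Daily Surveys section rule out the substitution:
- All parents receive the surveys, including controls, who get no intervention messages.
- Each response is paid, so a parent may answer surveys and ignore messages.
- Answering a survey does not show that a message was read.

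The gap between not opting out and using the messages would stay open after a survey table was added.

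**4. Whether message use is observable at all.** The overview of Aim 2 procedures describes messages being sent to parents. No reply or log-in is described, and under the Aim 1 methods only some messages carry links. In such a design, *active* in the sense of still receiving messages is a reasonable usage, and the protocol describes no other record of use that it fails to analyse.

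**5. Where daily-survey completion belongs.** Parents in the A-F plus P-F arm also face 42 × 2 = 84 randomizations. The share of the 84 surveys answered therefore describes how complete the proximal outcomes are in the exploratory MRT analysis. That bears on the feasibility of the MRT, not on the meaning of measure (3).

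**The case for a change.** The best case for a change is that it would be cheap and that the study's own aims invite it. Renaming measure (3) costs nothing, and percentages are often quoted without their parentheses. MRT feasibility is a stated purpose, yet neither the primary measures nor the exploratory analyses plan to report how many daily surveys were answered. The Methods section makes everything outside the Primary Analysis exploratory or ancillary, so coverage elsewhere cannot be presumed.

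Two parts of this stand. A report that drops the definition and writes of engagement would overstate what was measured. The omission of daily-survey completion is also real.

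Neither makes the plan wrong. The first is a matter of careful reporting of a term the protocol already defines. The second concerns data completeness, and anyone fitting the planned MRT regression to daily stress and affect must count the observed outcomes and would ordinarily report that count.

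An added table would also need a rule that the protocol does not supply. Surveys arrive by text too, and it is not stated whether a request to stop messages also stops the surveys. If it does, counting all 84 as scheduled would mix opt-outs into survey response in the texting arms and blur the comparison with control.

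**Conclusion.** The concern does not call for a change. Measure (3) is a correctly specified, openly defined non-opt-out rate with a clear denominator. It is a legitimate descriptor of acceptability, and no decision rule in the protocol depends on it. A new name would be a wording preference that alters no result, and a survey-response table would not measure message use.

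The unreported completion of the 84 daily surveys per parent is a gap of a different kind, which analysts of the daily outcomes can be expected to fill. The four primary measures remain sound without it.

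The effect is on interpretation only. Its size cannot be determined from the documents; the 0 to 50 point range above rests wholly on assumed rates and on treating survey silence as inactivity, which the design does not support. The conclusion assumes that reports keep the protocol's definition attached to the figure. It does not depend on what the unseen 6-week feedback items ask; if they cover reading or using messages, the gap in the concern is smaller still.
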